#### 11.4.3 Grading Severity of Events

The Division of AIDS Table for Grading the Severity of Adult and Pediatric Adverse Events (DAIDS AE Grading Table), Version 2.0, November 2014 must be used and is available on the DAIDS RSC Web site at http://rsc.tech-res.com/safetyandpharmacovigilance/.

#### 11.4.4 Expedited AE Reporting Period

- The expedited AE reporting period for this study is as per the EAE manual.
- After the protocol-defined AE reporting period, unless otherwise noted, only suspected, unexpected serious adverse reactions (SUSARs), as defined in Version 2.0 of the EAE Manual, will be reported to DAIDS if the study staff become aware of the events on a passive basis (from publicly available information).

#### 12.0 PARTICIPANTS

#### 12.1 Institutional Review Board (IRB) Review and Informed Consent

This protocol and the informed consent document (Appendix I) and any subsequent modifications will be reviewed and approved by the IRB responsible for oversight of the study. A signed consent form will be obtained from the participant (or person with power of attorney for participants who cannot consent for themselves). The consent form will describe the purpose of the study, the procedures to be followed, and the risks and benefits of participation. A copy of the consent form will be given to the participant, or legal guardian, and this fact will be documented in the participant's record.

# 12.2 Participant Confidentiality

All laboratory specimens, evaluation forms, reports, and other records that leave the site will be identified by coded number only to maintain participant confidentiality. All records will be kept locked. All computer entry and networking programs will be done with coded numbers only. Clinical information will not be released without written permission of the participant, except as necessary for monitoring by the ACTG, IRB, NIAID, OHRP, other government agencies as part of their duties, investigator, or the industry supporter or designee.

# 12.3 Study Discontinuation

The study may be discontinued at any time by the ACTG, IRB, NIAID, OHRP, the industry supporter, or other government agencies as part of their duties to ensure that research participants are protected.

#### 13.0 PUBLICATION OF RESEARCH FINDINGS

Publication of the results of this trial will be governed by ACTG policies. Any presentation, abstract, or manuscript will be made available for review by the industry supporter prior to submission.

# 14.0 BIOHAZARD CONTAINMENT

As the transmission of HIV and other blood-borne pathogens can occur through contact with contaminated needles, blood, and blood products, appropriate blood and secretion precautions will be employed by all personnel in the drawing of blood and shipping and handling of all specimens for this study, as currently recommended by the Centers for Disease Control and Prevention and the National Institutes of Health.

All dangerous goods and materials, including diagnostic specimens and infectious substances, must be transported using packaging mandated by CFR 42 Part 72. Please refer to instructions detailed in the International Air Transport Association (IATA) Dangerous Goods Regulations.

## GLOSSARY OF PROTOCOL-SPECIFIC TERMS

ART antiretroviral therapy

CLIA Clinical Laboratory Improvement Amendments

COX-2 cyclooxygenase-2
CVD cardiovascular disease
DSS dextran sulfate sodium
FXR farnesoid X receptor

GALT gut-associated lymphoid tissue

GLP-1 glucagon-like peptide-1

HBV hepatitis B virus HCV hepatitis C virus

HDL high-density lipoprotein cholesterol
HOMA-IR homeostatic model assessment
hsCRP high-sensitivity c-reactive protein
IBD inflammatory bowel disease
IBS irritable bowel syndrome

ICAM-1 intercellular adhesion molecule 1

IFNα interferon alpha IFNγ interferon gamma IHC immunohistochemistry

IL-6 interleukin 6 IL-10 interleukin 10

MIP-1α macrophage inflammatory protein 1 alpha

iNOS inducible nitric oxide synthase
LBP lipopolysaccharide-binding protein
LDL low-density lipoprotein cholesterol

LMR lactulose/mannitol ratio LPS lipopolysaccharides MPO myeloperoxidase

NASH nonalcoholic steatohepatitis
OI opportunistic infection
POC point of care testing

PPARy peroxisome proliferator-activated receptor gamma

RANTES regulated on activation, normal T-cell expressed and secreted

RCT randomized controlled trial

sCD14 soluble CD14 sCD163 soluble CD163 Th1 t helper cell 1 TLR-2 toll-like receptor 2 TLR-4 toll-like receptor 4 TMA trimethylamine

TMAO trimethylamine N-oxide TNFα tumor necrosis factor alpha

UC ulcerative colitis
VDR vitamin D receptor

### **SCHEMA**

### A5352s

Effects of the Probiotic Visbiome Extra Strength on Epithelial Barrier Function and Inflammation in HIV-Infected Participants on Suppressive Antiretroviral Therapy: A Substudy of A5350

DESIGN A5352s is a substudy of A5350 to evaluate whether there is a significant

change in intestinal permeability and mucosal inflammation after 24

weeks of probiotic Visbiome Extra Strength therapy.

DURATION Participants will be on the substudy for 26 weeks.

SAMPLE SIZE 40 participants: 20 participants from Arm A (Visbiome Extra Strength) and

20 participants from Arm B (placebo).

POPULATION A5350 participants who commit to undergo two flexible sigmoidoscopies

and biopsies and who have no contraindications for sigmoidoscopy.

INTERVENTION Participants will undergo a flexible sigmoidoscopy as part of the entry

visit, prior to starting Visbiome Extra Strength treatment. A second sigmoidoscopy will be performed at week 24. Participants will also undergo two lactulose/mannitol tests to evaluate change in gut

permeability.

### 1.0 HYPOTHESIS AND STUDY OBJECTIVES

## 1.1 Primary Hypothesis

After administration of Visbiome Extra Strength, CD4+ T-cells in the colon will increase.

## 1.2 Secondary Hypotheses

- 1.2.1 After administration of Visbiome Extra Strength, CD8+ T-cells in the colon will increase.
- 1.2.2 After the administration of Visbiome Extra Strength, neutrophil infiltration in the colon will decrease.
- 1.2.3 After administration of Visbiome Extra Strength, increased numbers of CD4+ T-cells in the colon will express the cytokine IL-17.
- 1.2.4 After administration of Visbiome Extra Strength, there will be a reduction in microbial translocation.
- 1.2.5 After administration of Visbiome Extra Strength, markers of gut permeability as measured by the Lactulose/Mannitol test will improve.
- 1.2.6 Visbiome Extra Strength administration will increase gastrointestinal microbial diversity from colonic mucosa samples.
- 1.2.7 Visbiome Extra Strength administration will change mucosal microbial metabolism of phosphatidylcholine, resulting in decreased trimethylamine (TMA) and trimethylamine N-oxide (TMAO).

# 1.3 Primary Objective

To assess total numbers of CD4+ T-cells per area by immunohistochemistry (IHC) from colonic tissue biopsies after Visbiome Extra Strength administration.

# 1.4 Secondary Objectives

- 1.4.1 To assess total numbers of CD8+ T-cells per area by IHC from colonic tissue biopsies after Visbiome Extra Strength administration.
- 1.4.2 To assess changes in neutrophil infiltration quantified by myeloperoxidase staining per area in colonic mucosa by IHC after Visbiome Extra Strength administration.
- 1.4.3 To assess changes in expression of cytokines IL17 by CD4+ T-cells per area by IHC after Visbiome Extra Strength administration.

- 1.4.4 To assess changes in microbial translocation by enumerating bacterial products (LPS and 16sRNA) per area within the lamina propria by IHC after Visbiome Extra Strength administration.
- 1.4.5 To assess measures of gut permeability after administration of the probiotic with the Lactulose/Mannitol Test after Visbiome Extra Strength administration.
- 1.4.6 To assess change in microbial diversity via 16S rRNA sequencing from the colonic mucosal samples after Visbiome Extra Strength administration.
- 1.4.7 To assess changes in mucosal microbial metabolism of phosphatidylcholine, resulting in decreased TMA and TMAO after Visbiome Extra Strength administration.

# 1.5 Exploratory Objectives

1.5.1 To assess changes in mucosal microbial metabolism by metabolomics and transcriptional analysis.

## 2.0 INTRODUCTION

## 2.1 Background

HIV-related intestinal dysbiosis contributes to CD4+ T-cell depletion, and chronic inflammation [1-3]. While the depletion of CD4+ T-cells occurs in the peripheral blood, it is most profound and persistent in the gut-associated lymphoid tissue (GALT). In nonhuman primate models, 90% of CD4+ T-cells are depleted from the GALT within 2 weeks of acute simian immunodeficiency virus (SIV) infection [4]. Similar findings have been reported with HIV infection [5]. Notably, ART initiation leads to incomplete reconstitution of intestinal mucosal CD4+ cells [6-9]. This failure to reconstitute the GALT leaves an individual susceptible to invasion of bacterial pathogens, enhanced local innate immune cell activation, and microbial translocation with consequent persistent systemic inflammation [10]. The study by Mehandru et al is particularly informative [7]. The research team identified persons with acute or early HIV infection and demonstrated the massive depletion of mucosal CD4+ T-cells early in infection. Even after 1-7 years of ART, 70% of HIV-infected individuals maintained a 50-60% depletion of mucosal lymphocytes despite complete viral suppression. The table below demonstrates the limited reconstitution of mucosal CD4 T-cells in different groups of individuals based on duration of ART treatment:

Participant Group	HIV Treatment	PBMC CD4%	MMC CD4%
HIV negative (n=18)	NA	59.6% + 14.3%	56.4% + 8.8%
HIV infected (n=32)	Before treatment	41.5% + 12.9%	19.3% + 8.8%
HIV infected (n=7)	After ~1 year of ART	46.9% + 10.1%	27.8% + 14.5%
HIV infected (n=7)	After 3-7 years ART	58.1% + 12.3%	42.3% + 3.1%

These data indicate that ART alone will not reconstitute the mucosal CD4+ lymphocytes and that the identification of adjunctive therapies that restore these cells may have the potential to also restore mucosal immune health in HIV-infected persons.

Notably, it is not only the dysbiosis that contributes to persistent inflammation, but also the downstream subsequent effects on gut permeability that likely facilitates excess bacterial translocation and heightened systemic inflammation. For example, Chung et al. recently demonstrated that intestinal epithelial damage, manifested by decreased colonic epithelial tight junction proteins enhances colonic permeability and thus, microbial translocation despite suppressive ART [11]. Several studies have demonstrated a shift from Bacteroidales dominant microbiome to more Prevotella in HIVinfected individuals, potentially leading to a decrease in production of short chain fatty acids such as butyrate [12-15]. Butyrate appears to be important as both an energy source for colonic epithelial cells and also as a downregulator of inflammation through inhibition of histone deacetylase and activation of G-protein coupled receptors [16, 17]. One potential alternative to intestinal antibiotics would be to utilize probiotics to repair intestinal damage through increased production of butyrate to improve mucosal immune function and to decrease microbial translocation. Indeed, topical butyrate has been demonstrated to improve outcomes in humans with refractory UC and rats with sulfonic acid induced colitis [18, 19]. Visbiome in particular has been demonstrated to increase levels of butyrate in mice [20].

In A5350, we propose an innovative intervention to reduce the chronic immune activation and inflammation by reversing the dysbiosis seen with HIV infection, by Visbiome Extra Strength administration. In this substudy (A5352s), we will perform flexible sigmoidoscopies before and after Visbiome Extra Strength administration to assess for changes in the gut mucosa and GALT. We hypothesized that administration of this probiotic will facilitate reconstitution of a healthy, diverse microbiome and have significant potential for repairing mucosal integrity and immune function via reconstitution of mucosal CD4+ T-cells and APCs, repair of intestinal damage, and improved epithelial tight junctions. The functionality of these histochemical changes will be tested via two methods. First, we will administer non-absorbed sugars to determine the level of gut permeability via the Lactulose/Mannitol test. Second, we will assess for recovery of CD4+ and CD8+ T-cells and reduction in mucosal inflammation via colonic biopsies. Identifying whether this approach restores a healthy microbiome in HIV-infected persons and positively impacts mucosal function to reduce chronic immune activation will greatly enhance our understanding of the interface between the microbiota, the immune system, and overall health.

### 2.2 Rationale

We propose to conduct a phase II, randomized two-arm substudy with Visbiome Extra Strength and matching placebo in HIV-infected participants on stable ART with CD4+ count >200 cells/mm³ and plasma HIV RNA <50 copies/mL, to better understand the effects of this probiotic product on colonic mucosal histopathology, immune function, and barrier function. This is a substudy of A5350, in which participants will undergo sigmoidoscopy to obtain colonic biopsy tissue, as well as additional testing of mucosal barrier function.

### 3.0 STUDY DESIGN

A5352s is a substudy of A5350 that will enroll HIV-infected participants ≥18 years of age, who have been on stable ART for at least 24 weeks prior to study (A5350) entry, and have a CD4+ T-cell >200 cells/mm³ prior to study entry and plasma HIV RNA <50 copies/mL for 48 weeks prior to study entry.

The primary objective of the substudy is to determine whether there is a significant change in colonic CD4+ T-cell count per area after administration of probiotic Visbiome Extra Strength therapy.

A total of 40 participants from A5350 will be included, 20 from Arm A (Visbiome Extra Strength + stable ART; treatment arm) and 20 from Arm B (placebo for Visbiome Extra Strength + stable ART; control arm). Participants will be on the substudy for a total of 26 weeks. Probiotic Visbiome Extra Strength or placebo will be administered from week 2 through week 26. Colonic biopsies collected by flexible sigmoidoscopy will be obtained per the SOE to assess tissue-specific effects related to immunologic outcomes, inflammation, bacterial translocation, and gut integrity. Any incidental clinical findings will be followed up at the time of the procedure if possible (eg, removal of incidental polyps or biopsy of abnormal lesions). All abnormal findings will be referred for further appropriate care under the direction of the site gastroenterologist. Participants will also undergo two Lactulose/Mannitol tests to evaluate gut permeability. Further details about these procedures are included in the study MOPS.

## 4.0 SELECTION AND ENROLLMENT OF PARTICIPANTS

## 4.1 Inclusion Criteria

## 4.1.1 Enrollment in A5350

- 4.1.2 The following laboratory values obtained within 45 days prior to entry by any US laboratory that has a CLIA certification or its equivalent:
  - Platelet count ≥100,000/mm³
  - INR ≤1.3
  - Partial thromboplastin time (PTT) <2x upper limit of normal (ULN)

4.1.3 Ability and willingness of participant or legal guardian/representative to provide informed consent.

### 4.2 Exclusion Criteria

- 4.2.1 Diagnosis with gastrointestinal disease such as inflammatory bowel disease or irritable bowel syndrome.
- 4.2.2 Bleeding diathesis or requirement for anticoagulation that would increase the risk of sigmoidoscopy and biopsy.
- 4.2.3 History of anal, rectal, or colon cancer.
- 4.2.4 Any prior surgical procedure requiring repair, excision, or bypass of the intestinal tract.
  - NOTE: Surgery for excision of condyloma is allowed.
- 4.2.5 Use of clopidrogel (Plavix), warfarin (Coumadin), or other blood thinners that cannot be stopped for clinical reasons for 5 days before and 5 days after the sigmoidoscopy with colonic biopsies.
- 4.2.6 Use of aspirin and /or nonsteroidal anti-inflammatory drugs (NSAIDs) that cannot be stopped for clinical reasons for a minimum of 7 days before and after the sigmoidoscopy with colonic biopsies, and at least 7 days before the lactulose/mannitol gut permeability test.
- 4.3 Substudy Enrollment Procedures

As specified in the main study, A5350. To optimize expeditious enrollment in the substudy, one of every three participants at an individual site enrolled in the parent study must also agree to participate in the substudy.

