#### Section 4.1.8 is revised to:

For females of reproductive potential, negative serum or urine pregnancy test (latter with a sensitivity of ≤25 mlU/mL) within 45 days prior to entry by any US clinic or laboratory that has a CLIA certification or its equivalent, or is using a point-of-care (POC)/ CLIA-waived test, or at any network-approved non-US laboratory or clinic that operates in accordance with Good Clinical Laboratory Practices (GCLP) and participates in appropriate external quality assurance programs.

Note: Reproductive potential is defined as girls who have reached menarche and pre-menopausal women who have not had a sterilization procedure (eg hysterectomy, bilateral oophorectomy, tubal ligation, or salpingectomy), Women are considered menopausal if they have not had a menses for at least 12 months and have a FSH of greater than 40 IU/L, or if FSH testing is not available, they have had amenorrhea for 24 consecutive months. Acceptable documentation of a sterilization procedure and menopause is patient-reported history.

The above information will be incorporated into the next protocol version as necessary if the protocol is amended.

The following are changes to A5352s, Version 1.0, 01/05/16 (changes are noted in bold or strikethrough):

 Section 6.1 Schedule of Events is revised to remove the hematology evaluation from the week 24 visit.

	Screening			Post-Entry On Treatment		
Evaluation	(within 45 days prior to substudy entry)	Entry	Week 1 (±4 days)	Week 24 (at least 14 days prior to week 26) (±7 days)	Week 26 (±7 days)	
Hematology	Х			×		

Section 6.3.2 Laboratory Evaluations is revised to:

At screening, and week 24, all hematology laboratory values are recorded in the source document only.

Hematology INR and PT/PTT

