## 5.1 Prohibited Medications

Use of the following medications during the substudy are prohibited:

- Aspirin, antiplatelet agents, NSAIDs which cannot be held as above for flexible sigmoidoscopy and lactulose/mannitol gut permeability test.
- Medications as specified in the main study, A5350.

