### Entry

Entry evaluations must be completed at least 24 hours after screening evaluations.

NOTE: At the time of a sigmoidoscopy visit, the participant must avoid drinking alcohol or taking nonsteroidal anti-inflammatory medications, including aspirin or any blood thinners for 7 days prior to the test.

### Week 1

Week 1 evaluations must be completed at least 4 days after entry evaluations unless otherwise specified.

NOTE: At the time of a sugar absorption test visit, the participant must have avoided drinking alcohol for 3 days prior to the test, avoided taking nonsteroidal

anti-inflammatory medications, including aspirin or any blood thinners for 7 days prior to the test, and have abstained from exercise the day before and the morning of the test.

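### A5352s exclusion 4.2.5 screens for a shorter blood-thinner hold than the visit notes require before sigmoidoscopy, and for no hold before the sugar test

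*Protocol*

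**What the plan says.** Four places in the A5352s protocol govern blood thinners around the procedures.

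- **Exclusion 4.2.5** names clopidogrel, warfarin and other "blood thinners that cannot be stopped for clinical reasons for 5 days before and 5 days after the sigmoidoscopy". The sugar test is not mentioned.
- **Exclusion 4.2.6**, for aspirin and NSAIDs, uses a different interval and covers both procedures: "a minimum of 7 days before and after the sigmoidoscopy with colonic biopsies, and at least 7 days before the lactulose/mannitol gut permeability test".
- **The visit notes in 6.2.1** say that anyone coming for sigmoidoscopy "must avoid drinking alcohol or taking nonsteroidal anti-inflammatory medications, including aspirin or any blood thinners for 7 days prior to the test". For the sugar test the participant must have avoided "anti-inflammatory medications, including aspirin or any blood thinners for 7 days prior to the test, and have abstained from exercise" around the test. Clarification Memo #1 repeats the 7-day sugar-test rule for Week 1 and states it for Week 26.
- **Section 5.1** prohibits, during the substudy, "Aspirin, antiplatelet agents, NSAIDs which cannot be held as above for flexible sigmoidoscopy and lactulose/mannitol gut permeability test".

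Two further exclusions or limits bear on who is affected. Exclusion 4.2.2 removes people with a bleeding diathesis or a need for anticoagulation that raises procedural risk, and 4.1.2 requires an INR of at most 1.3 at screening.

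**The concern.** For one class of drug, eligibility and the visit notes give different answers. Eligibility asks whether the drug can be interrupted for 5 days on either side of sigmoidoscopy. The visit notes then ask for 7 days before sigmoidoscopy and, separately, 7 days before each sugar test. A person can be cleared against the first standard and fail the second.

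The mismatch lies in 4.2.5. The aspirin/NSAID criterion, 4.2.6, already agrees with the visit notes for both procedures.

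Two things are at stake. One is participant safety: sites need one consistent instruction on how long a blood thinner is interrupted around a biopsy. The other is endpoint data. A cancelled biopsy costs that participant's primary substudy outcome (9.2.1), and a cancelled sugar test costs the permeability outcome (9.2.2.5). The substudy plans on 16 evaluable participants per arm out of 20. Its main analysis (9.6) also drops anyone who used a prohibited medication, and that is hard to adjudicate for an antiplatelet agent if 5.1 refers to a hold that is not stated.

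**Working it through.** No sample size, power or error rate is involved, and the plan gives no figure to reproduce. The check is a day count.

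**Inputs**

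- Hold screened by 4.2.5: day −5 to day +5, with sigmoidoscopy on day 0 and that day counted as held.
- Hold required by the visit notes: the 7 days before each procedure.
- Week 1 visit: nominal day 7 with a window of ±4 days (6.1), so days 3 to 11 if the entry sigmoidoscopy is on the entry day.
- Minimum spacing of the sugar test after sigmoidoscopy: 7 days (6.3.3). Section 6.2.1 separately gives a 4-day minimum between entry and Week 1 evaluations.
- Second sigmoidoscopy: at least 14 days before Week 26 (6.1).

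**Formula**

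For a procedure on day d, the required days are R(d) = {d−7, …, d−1}. The screened days are S = {−5, …, +5}. The unscreened days are those in R(d) but not in S.

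| Procedure | d | Required days | Unscreened days | Count |
|---|---|---|---|---|
| Sigmoidoscopy | 0 | −7 to −1 | −7, −6 | 2 of 7 |
| Week 1 sugar test, earliest under 6.3.3 | 7 | 0 to 6 | 6 | 1 of 7 |
| Week 1 sugar test, end of window | 11 | 4 to 10 | 6 to 10 | 5 of 7 |
| Week 26 sugar test, earliest | 14 | 7 to 13 | 7 to 13 | 7 of 7 |

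From day 7 to day 11 the count is d − 6, so it runs from 1 to 5. For Week 26, d is 14 or more. The required days then all fall after day +5, so 4.2.5 screens none of them.

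On days 4 to 6, which the 4-day minimum would allow but 6.3.3 would not, the required days run from −3 to 3 (d = 4) up to −1 to 5 (d = 6). These lie wholly inside S, so the sugar test adds no gap there. The 2-day gap before sigmoidoscopy remains.

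**Section 5.1 against what precedes it**

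It refers back to earlier holds for both procedures. For aspirin and NSAIDs, 4.2.6 supplies both. For other antiplatelet agents, such as the clopidogrel named in 4.2.5, only a sigmoidoscopy hold is stated, so the sugar-test reference points to nothing. Anticoagulants, represented in 4.2.5 by warfarin, are not named in 5.1.

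**The case against.** The best defence is that the affected group is very small. It must contain someone who takes a blood thinner, is not removed by 4.2.2, has an INR of at most 1.3 at screening, and can stop for 5 or 6 days but not 7, or cannot hold the drug for a sugar test. This stands as a limit on size. It does not empty the group: 4.2.2 states no interval and does not clearly reach antiplatelet agents, and 4.2.5 itself contemplates users who can stop.

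It can also be said that eligibility sets only a floor and the visit note controls. In that case eligibility does not screen for what the visits demand, which is the point. Procedural detail is deferred to the study MOPS, which is not among the documents. It may be clearer there, but the protocol text would still disagree with itself.

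A reader might infer that a site is bound to break one rule or lose the endpoint. The documents do not support that for the sugar test, because Clarification Memo #1 lets the site ask the core team whether to proceed. That route lists alcohol, NSAIDs and exercise, not blood thinners. Since the note folds blood thinners into the NSAID clause, coverage is arguable in either direction. No such route is written for sigmoidoscopy.

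A reader might also see a contradiction in Letter of Amendment #1, where "Section 6.1 Schedule of Events is revised to remove the hematology evaluation from the week 24 visit", so that INR and PTT are not rechecked before the second biopsy. That was a deliberate change. A screening limit for enrolment does not promise a retest, so it is no part of this point.

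**Conclusion.** The inconsistency is real, confined to A5352s, and minor. For blood thinners, 4.2.5 and the visit notes differ by 2 days before sigmoidoscopy, by 1 to 5 days before a Week 1 sugar test done 7 to 11 days after sigmoidoscopy, and by all 7 days before the Week 26 sugar test. Section 5.1 does not close the gap.

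The counts assume that the entry sigmoidoscopy is on the entry day and that the procedure day counts as held. Without the second assumption, only the day-7 figure changes, from 1 to 2. The sigmoidoscopy note sits under the Entry heading but is worded for any sigmoidoscopy visit; applying it to Week 24 rests on that wording, since 6.2.2 has no note of its own.

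It is tempting to add the intervals into one total of days off treatment and compare that with the 5 + 5 = 10 days in 4.2.5. The documents do not support such a total. The spacing between sigmoidoscopy and sugar test is given in two ways, and the days after sigmoidoscopy come from the eligibility rule, not the visit notes. How many participants would be affected cannot be derived.

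**What to change.** By clarification memo or letter of amendment, reconcile A5352s 4.2.5, 5.1, the 6.2.1 notes and the Clarification Memo #1 text for Weeks 1 and 26:

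- The interval for which a blood thinner must be stoppable to be eligible should equal the interval the visit notes require, stated separately for sigmoidoscopy and for the sugar test.
- Section 5.1 should cover the same drug classes as 4.2.5 and refer to holds that are actually stated.
- The memo's core-team route should say whether it covers blood thinners.
- The 4-day minimum in 6.2.1 and the 7-day minimum in 6.3.3 should be reconciled. The 6.2.1 text allows for other specification, so 6.3.3 may be meant to govern, but this should be said.

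The study clinicians must choose the intervals; none is proposed here. The cost is wording changes and, depending on the choice, possibly slightly fewer eligible substudy candidates. No change to the sample size or analysis follows.
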